4. METHODOLOGY

4.1. Study Population

Minimum criteria for enrollment will be the following:

- Exposure classification:
 - For belimumab exposed pregnant women:

Sufficient evidence to confirm that exposure to commercially supplied belimumab occurred within the 4 months prior to and/or during pregnancy ("belimumab exposed")

Or

• For belimumab unexposed pregnant women:

Sufficient evidence to confirm that exposure to belimumab did not occur within 4 months prior to and / or during pregnancy ("unexposed")

• Sufficient information to classify the pregnancy report as prospective or retrospective (Section 4.6.8.1 and Section 4.6.8.2). Retrospective reports of pregnancy are those in which the pregnancy ended before enrollment or at the time of first contact with the registry. Two definitions for prospective reports of pregnancy will be used in this registry, traditional prospective and pure prospective:

Traditional prospective reports of pregnancy will include all women who enroll in the registry before the end of pregnancy (live birth, fetal loss, etc), regardless of known normal or abnormal prenatal test results

Pure prospective reports of pregnancy are a subset of traditional prospective reports and include those where (a) the enrollee did not know at the time of enrollment whether the fetus had a malformation, and (b) no prenatal testing was completed prior to enrollment.

- Full initial reporter (i.e., pregnant woman or HCP) contact information to allow for follow-up (name, address, telephone number/email address) and contact information for applicable HCPs if initial reporter is the pregnant woman
- Consent provided by the pregnant woman for her participation and assent for participation of her infant

Reported cases that do not meet the minimum criteria for registry enrollment will be ineligible for inclusion in the registry and will not be entered into the database. In such cases, the report will be forwarded to GSK and handled using routine pharmacovigilance measures.

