4.3. Outcome Definitions

4.3.1. Pregnancy Outcomes of Interest

The following pregnancy outcomes will be collected by the registry:

- Spontaneous miscarriage: fetal death or expulsion of products of conception prior to 20 weeks' (<20 weeks) gestation
- Live birth: the birth of a living fetus at 20 weeks' gestation or greater (\geq 20 weeks), or, if gestational age is unknown, a fetus weighing 500 g or more (\geq 500 g)
- Stillbirth: a fetal death occurring at 20 weeks' gestation or greater (≥20 weeks), or, if gestational age is unknown, a fetus weighing 500 g or more (≥500 g)
- Elective termination: voluntary interruption of pregnancy, including pregnancy termination that occurs electively, to preserve maternal health, or due to fetal abnormalities
- Preterm birth: an infant born at gestational age less than 37 weeks (<37 weeks)
- Neonatal death: an infant who after live birth expired within the first 28 days (≤28 days) of life
- Ectopic pregnancy: implantation of a conception outside of the uterus
- Molar pregnancy: a conception that results in a gestational trophoblastic tumor
- Small for gestational age (SGA): defined as an infant whose birth weight is less than the 10th percentile for the gestational age. It is based on data derived from an appropriate reference population. The registry will utilize the sex specific international growth reference standards from the International Fetal and Newborn Growth Consortium for the 21st Century (INTERGROWTH-21st) for those born at ≥33 weeks gestational age (Villar, 2014). The INTERGROWTH-21st standards are the latest available global reference standards, representing contemporary information from an international, multiethnic, diverse population and have been specifically developed for modern research. As the INTERGROWTH-21st standards are valid for infants born between 33^{0/7} and 42^{6/7} weeks gestation, SGA will be additionally classified using the reference standard endorsed by the American Congress of Obstetricians and Gynecologists (ACOG) which is applicable for the entire range of gestational age (Alexander, 1996).

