4.6. Data Collection and Management

This is a voluntary registry and the registry awareness program will encourage enrollment as early in pregnancy as possible, so as to minimize bias. In addition, all investigators from the SABLE protocol will be made aware of the Registry and will inform eligible women of their option to co-participate in this Registry. The participants will be followed for the duration of their pregnancies and after birth to ascertain pregnancy and infant outcomes.

The pregnant woman and appropriate members of her health care team will serve as data reporters to the registry. Data regarding participants' SLE disease severity will be sought from the belimumab prescriber to encompass 4 different timepoints (pre-conception, registration, end of second trimester and pregnancy outcome). Data regarding the pregnancy and pregnancy outcome will be sought from the obstetric HCP, and data on live-born infants will be sought from the pediatric HCP. Appropriate members of the woman's and infant's health care team will be contacted to complete missing data as

needed. Participant-reported data will be verified from the HCP overseeing that component of the participant's care. All data will be collected from the participant or the relevant HCP on case report forms (CRF). Medical records will not be requested by the registry unless considered appropriate during targeted follow-up of specific events and outcomes (see Section 4.6.5).

As noted in the following table (Table 1), contact will be made with HCPs at several different time points. Contact with the providers will be timed to maintain interest in the data collection and to minimize loss to follow up. CRF data collection will allow entry of data regardless of when it is obtained and will be associated with gestational age, not with date entered in the CRF. Much of the data collected will be recorded on running logs to facilitate complete data capture.

- Depending on the gestational age at time of enrollment and pregnancy outcome, not all CRFs may be completed for each participant. For example, if a participant enrolls late in pregnancy and delivers early, there may be no second trimester data collection form completed. Additional contacts may occur at the discretion of registry personnel or HCP to complete data collection. At each contact, data from every visit to the HCP since the prior contact between the HCP and the registry will be reviewed for relevance to the registry.

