4.6.8. Registry Case Management and Disposition

4.6.8.1. Prospective Registry Reports

The registry will encourage prospective registration, which is defined as those exposures registered before the end of the pregnancy (i.e., live birth, fetal loss, etc). Two definitions for prospective reports of pregnancy will be used in this registry, traditional prospective and pure prospective [Holmes, 2008; Tomson, 2004]. Traditional prospective reports of pregnancy will include all women who enroll in the registry before the end of pregnancy (live birth, fetal loss, etc), regardless of known normal or abnormal prenatal test results. Pure prospective reports of pregnancy are a subset of traditional prospective reports and include those where (a) the enrollee did not know at the time of enrollment whether the fetus had a malformation, and (b) no prenatal testing was completed prior to enrollment. Reports of pregnancy defined as pure prospective will be included in the primary study population. Section 6 addresses the rationale, potential bias, and analytic techniques that may be employed to attempt to control for any known bias that may be introduced by this practice.

Prospective infant follow-up beyond the first year of life will not be routinely solicited by the registry but follow-up may be extended on a case-by-case basis if deemed medically necessary. In addition, while the study remains active, reports of birth defects that were identified in children after the 1st year of life and by 6 years of age will be entered into the database and reported in registry reports. This age criterion is consistent with CDC MACDP practice (see CDC MACDP Case Definition Criteria, 2015). Prospective reports of birth defects in infants beyond the first year of life and by 6 years of age will not be included in the primary study population, but will be described in the text of the registry final report. Prospective reports of infant infections beyond the first year of life will be forwarded to the sponsor for pharmacovigilance purposes only.

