4.8.4.1. Adverse Pregnancy Outcomes

The registry will identify the number of cases of spontaneous miscarriages, elective terminations, stillbirths, preterm births, and SGAs; proportions of these outcomes will be calculated with 95% confidence intervals (CIs). The denominator for the proportion of spontaneous miscarriages will be those pregnancies enrolled prior to the 20th week of gestation. Because the prevalence of spontaneous miscarriages in pregnancy registries is heavily influenced by the timing of registry enrollment [Roberts, 2009], the analysis of spontaneous miscarriages will be stratified by gestational age at enrollment. Because the prevalence of preterm birth and low birth weight is elevated in multiple gestations, these cases will be excluded from the analysis of preterm birth and / or low birth weight outcomes.

Categorization of variables for stratification, such as earliest trimester of exposure, maternal age at enrollment, and gestational age at enrollment, will be described in the RAP.

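### The preterm-birth proportion has no enrollment-timing limit, so in the traditional prospective set late enrollees who cannot, or can hardly, be events dilute it

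*Protocol*

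**What the plan says.** Protocol Section 4.8.4.1 lists miscarriage, elective termination, stillbirth, preterm birth and SGA as outcomes to be reported as proportions with 95% confidence intervals. For miscarriage it fixes the denominator as "those pregnancies enrolled prior to the 20th week", and it adds stratification because enrollment timing strongly influences that rate. For preterm birth it states one restriction, on multiple gestations: "these cases will be excluded from the analysis of preterm birth". It gives no limit on week of entry.

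Section 4.3.1 defines preterm birth as birth before 37 completed weeks. Section 4.6.8.1 says of traditional prospective reports that they "will include all women who enroll in the registry before the end of pregnancy". Section 4.6 expects late entry; one of its examples is "if a participant enrolls late in pregnancy and delivers early".

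Two provisions soften the point. Section 4.8.1 names gestational age at enrollment as a stratification variable, with categories left to the Reporting and Analysis Plan (RAP). Section 4.8.2 makes the pure prospective cases the primary population, and these must enroll before any prenatal test. The Glossary counts ultrasound as such a test.

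**The concern.** This is left truncation. A woman who enrolls at 38 weeks has already passed the period in which a preterm birth could occur. One who enrolls at 32 weeks cannot contribute a birth before 32 weeks. Women who delivered earlier had less time to enroll and are under-represented. The protocol recognizes this mechanism for miscarriage and corrects it in the denominator, but it leaves the next outcome in the same paragraph uncorrected.

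Preterm birth is a named secondary outcome (Section 2.2). Section 4.8.4 bases comparisons with external SLE cohorts on the observed frequency and the lower 95% limit. Section 4.8.4.3 says external comparison will be considered for all outcomes where data exist. A proportion lowered by recruitment timing makes an excess harder to see, which is the unwelcome direction for a safety registry.

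**Working it through.** **Figures the protocol states.** It gives none for preterm birth. Its live-birth counts reproduce: 500 × 0.95 × 0.80 = 380 and 500 × 0.83 × 0.75 = 311.25. So does its exact interval for birth defects: 350 × 0.0278 = 9.73 events gives 1.32% to 5.09%. I use 350 live births below only as a convenient size.

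**Inputs.** True preterm proportion P = 40%, the SLE background figure in Section 1.1. The timing of enrollment and of preterm births is not in the protocol and is assumed.

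**Step 1: women enrolled at or after 37 weeks.** If they make up a share f of counted births and all others carry full risk, the expected proportion is P(1 − f).
- f = 2%: 40% × 0.98 = 39.2%
- f = 5%: 40% × 0.95 = 38.0%

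**Step 2: women enrolled before 37 weeks but after some preterm births would have occurred.** If a share h of preterm births precedes entry, the remaining risk is P(1 − h)/(1 − Ph).
- h = 25%: 0.30/0.90 = 33.3%
- h = 50%: 0.20/0.80 = 25.0%

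**Step 3: both together, by simulation of 2,000,000 pregnancies.** Assumptions:
- Of preterm births, 20% fall at 24–29 weeks, 30% at 30–33 and 50% at 34–36.
- Term births are uniform over 37–42 weeks.
- Early entry is uniform over weeks 6–20 and late entry over weeks 20–41, independent of risk.
- Only women whose entry precedes delivery are counted.

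| Intended entries after week 20 | Overall proportion | Without entries ≥37 weeks | Share entering ≥37 weeks | Births lost, limit 24 weeks | Births lost, limit 20 weeks |
|---|---|---|---|---|---|
| 15% | 38.8% | 39.3% | 1.1% | 9% | 12% |
| 30% | 37.6% | 38.4% | 2.2% | 19% | 25% |
| 50% | 35.8% | 37.2% | 3.8% | 34% | 44% |
| Entry uniform over weeks 6–41 | 34.8% | 36.5% | 4.7% | 41% | 54% |

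The third column follows from the second and fourth; in the last row, 34.8/(1 − 0.047) = 36.5. Limiting entry to before week 20 or 24 returns 40.0%. Ending term births at 41 weeks instead raises the overall proportion by at most 0.3 points, to 38.9% in the first row and 35.1% in the last. Across the term-birth spreads tried, the loss at a 24-week limit reaches at most about 42%.

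**Step 4: scale.** The exact 95% interval for 140/350 is 34.8% to 45.3%, a half-width of about 5 points. The shift of about 1 to 5 points therefore runs from a fraction of a half-width to about one.

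**The case against.** **The protocol is silent rather than wrong, and the RAP may settle it.** The RAP was not available and could set a denominator. But the protocol itself fixes the denominators for miscarriage, birth defects and infant infections. For preterm birth it writes a specific exclusion that leaves out the timing limit applied in the same paragraph. Followed as written, the overall figure includes the late enrollees.

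**The primary population is largely protected.** This stands. Entry before any prenatal test, ultrasound included, makes late entry unlikely, though it is not forbidden. The effect falls mainly on the traditional prospective summary, which is planned separately and is the set to which the target of 500 refers.

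**Stratification is already planned.** It is, and Section 4.6 also promises to encourage early enrollment. Strata reveal the gradient. They do not correct the overall proportion and its interval.

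**The rate might not be understated.** A reader might infer that the bias can only be downward. Truncation alone acts that way, but Section 6 allows that high-risk or low-risk pregnancies may be preferentially reported. Women who enroll late because of complications could raise the proportion, so the direction depends on entry being unrelated to risk.

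**The 40% is not a benchmark.** A reader might treat it as the registry's comparator. It is background literature in Section 1.1. Section 5 says suitable external sources are still to be determined, and Section 4.8.3.2 warns that quantitative comparisons may be hard to interpret.

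**Conclusion.** The point holds for the overall preterm proportion, chiefly in the traditional prospective set. As written, Section 4.8.4.1 keeps women who cannot be events, and women with reduced remaining risk, in that figure. If entry timing is independent of risk, the shift is about 1 to 5 points down from a true 40% under the assumed patterns. The lower end applies if about 15% of intended entries come after week 20, the upper end if entry is spread evenly over weeks 6–41. The actual size is unknown because the protocol gives no enrollment-timing distribution.

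The documents do not support saying that the primary pure prospective result is materially biased, or that the registry will fail a fixed benchmark. This is a secondary descriptive outcome, but the correction is simple and uses dates already collected.

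**What to change.** In Section 4.8.4.1:

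1. Exclude women enrolled at or after 37 weeks from the preterm denominator in both the pure and the traditional prospective sets. Under the assumed patterns this drops about 1% to 5% of counted births. On its own it is not enough: the proportion still runs from 39.3% down to 36.5%.
2. Base the headline proportion on one of two options, named in advance:
   - singleton live births with early entry, for example before 20 or 24 weeks;
   - a left-truncated estimate on the gestational-age scale with entry at enrollment, which keeps later enrollees.
3. List later enrollees and their preterm births by week of entry.

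Neither week is the only sound choice. A 20-week limit matches the miscarriage rule and the protocol's lower bound for a live birth. A 24-week limit keeps more births; it returned 40.0% here because no births before 24 weeks were assumed.

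**Cost.** A few sentences and no new data. An early-entry limit loses about 9% to 42% of births at 24 weeks, or 12% to 54% at 20 weeks. By 1.96 × √(0.4 × 0.6/n), the half-width is 5.1 points at n = 350. A 9% loss (n ≈ 318) gives 5.4 points, a 42% loss (n = 203) 6.7 and a 54% loss (n = 161) 7.6. The widening is modest if few enroll late and appreciable if many do. The left-truncated estimate avoids most of this loss but, like the figures above, assumes entry timing is unrelated to risk.

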4.8.4.2. Birth Defects

The prevalence of birth defects reported to the registry will be calculated as the percentage of birth defects from the total number of live births. The differences between the observed registry birth defect rates and these comparators will be estimated along with 95% confidence intervals. Fetal losses with reported birth defects occurring at or after 20 gestation weeks will be included in the numerator of the estimate of risk for birth defects to increase sensitivity and to allow comparison post-outcome with the CDC MACDP and EUROCAT. The analysis will also be conducted including fetal losses with reported birth defects occurring at less than 20 gestational weeks in the calculation of risk. It is possible that the background birth defect rate in the overall population may be different from the birth defect rate in SLE patients. Accordingly, additional analyses using different appropriate external SLE comparator cohorts will also be performed.

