4.6.4. Infant Follow-Up

Pediatric Follow-up forms will be requested from the pediatric HCP for live-born infants at approximately 4 and 12 months of age:

- Date of assessment
- Weight, length and head circumference of the infant at birth if not provided at pregnancy outcome (at 4 month assessment)
- Infant date of birth
- Current weight
- Developmental milestones
- Birth defects identified
- History of serious and/or clinically significant infections and/or fevers of unknown origin since last contact, causative microorganisms if available, treatment, and outcomes
- Breastfeeding status
- Mother's belimumab or other SLE treatment exposure post-partum, if dosed while breastfeeding

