4.6.8.3. Lost to Follow-Up

For a prospective report or pregnancy where follow-up information on the pregnancy outcome, from a HCP, is never obtained, unavailable, and/or where the indication of a birth defect is designated as unknown, the pregnancy will be considered lost to follow-up. Cases lost to follow-up prior to pregnancy outcome will be tallied in the registry reports but not included in the primary study population. For infants, if pediatric follow-up information, from a HCP, is never obtained, unavailable, and/or where infant status is designated as unknown, the infant will be considered lost to follow-up. Any cases with infant outcome will be analyzed according to the length of infant follow up.

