4.6.8.4. Evaluable Registry Reports

An evaluable registry report is a case with data submitted or confirmed by a HCP that meets the minimum criteria for a registry report, as described in Section 4.1, and for which the pregnancy outcome is known. Pure prospective reported evaluable cases will

be included in the primary study population section of the registry report. Evaluable belimumab exposed traditional prospective and retrospective cases as well as unexposed cases will be summarized separately in the interim and final reports. Participant-reported data without HCP confirmation will also be summarized separately in the final report.

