4.8.2.1. Exclusions for Analysis Purposes

Invalid cases (Section 4.6.8.5), pregnancies deemed lost to follow-up, retrospective cases, cases where participants do not have SLE, and SLE patients not exposed to belimumab will be excluded from the primary belimumab study population.

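### The primary birth-defect prevalence counts defects found up to 12 months but divides by all live births, including infants with no follow-up after birth, and the MACDP comparison does not mention the differing age windows

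*Protocol*

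**What the plan says.** - **Estimate.** Protocol sections 4.8.1 and 4.8.4.2 define prevalence as "calculated as the percentage of birth defects from the total number of live births". Neither section makes the denominator depend on infant follow-up.
- **Who is in the denominator.** Under section 4.6.8.4 a case is evaluable when its data come from or are confirmed by an HCP, it meets the minimum criteria, "and for which the pregnancy outcome is known". The exclusions in section 4.8.2.1 include "pregnancies deemed lost to follow-up, retrospective cases, cases where participants do not have SLE". Infants lost to follow-up are not on that list.
- **Two kinds of loss.** In section 4.6.8.3, loss at pregnancy level covers the case "where the indication of a birth defect is designated as unknown, the pregnancy will be considered lost to follow-up". Loss at infant level is a separate category: "if pediatric follow-up information, from a HCP, is never obtained, unavailable, and/or where infant status is designated as unknown, the infant will be considered" lost. No consequence for the birth-defect denominator is attached to it.
- **When defects are collected.** Table 1 collects them at pregnancy outcome. After that, "Pediatric Follow-up forms will be requested from the pediatric HCP for live-born infants at approximately 4 and 12 months of age" (section 4.6.4), and these forms ask about defects.
- **Length of follow-up.** Section 4.6.8.3 says in general: "Any cases with infant outcome will be analyzed according to the length of infant follow up". Section 4.8.4.3 carries this into the infection tables. Section 4.8.4.2 does not mention it, and it is not among the subgroups in section 4.8.1.
- **Age limit.** Section 4.6.8.1 keeps defects found after the first year and by age 6 out of the primary population and describes them in the text of the final report. Of the age-6 limit it says: "This age criterion is consistent with CDC MACDP practice".

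**The concern.** The numerator runs to 12 months, while part of the denominator may have been observed only at birth. For those infants, a defect that becomes apparent at 3 or 10 months has no route into the numerator. The estimate then sits below the true 12-month prevalence, and the shortfall grows with infant-level loss.

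The one-year cut-off is a second and separate cause. It applies to every infant, including those fully followed, and it matters for the planned difference against the MACDP figure of 2.78%.

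Section 7.11 says that the registry is meant to identify signals of increased risk. For that purpose missed cases are the costly error.

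**Working it through.** **1. The plan's own figures.** Section 5 assumes 350 live births at 2.78%, which is 0.0278 × 350 = 9.73 expected cases. The Clopper-Pearson interval by beta quantiles with x = 9.73 and n = 350 is 1.325% to 5.093%, which matches the stated 1.32% to 5.09%. The MACDP rate is 6,945 / 249,999 = 2.778%, also as stated.

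**2. Model for the ascertainment gap.** Let p be the true prevalence, L the share of defects first recognised between the birth report and 12 months, and U the share of live-born infants with no later form. If loss is unrelated to defect status:

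reported rate = p × (1 − L × U)

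The protocol gives neither L nor U. I assume L = 20-50% and U = 20-25%. The range for U borrows the pregnancy-level loss in section 5. That loss has already been removed in reaching 311 to 380 live births, so using the same figure for infants is an assumption and not a protocol figure.

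| L | U | Reported rate | Relative change | Cases missed of 9.73 |
|---|---|---|---|---|
| 20% | 20% | 2.78% × 0.960 = 2.67% | −4% | 0.39 |
| 20% | 25% | 2.78% × 0.950 = 2.64% | −5% | 0.49 |
| 50% | 20% | 2.78% × 0.900 = 2.50% | −10% | 0.97 |
| 50% | 25% | 2.78% × 0.875 = 2.43% | −12.5% | 1.22 |

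**3. Size against the stated precision.** The shift is 0.11 to 0.35 percentage points. The stated interval reaches 2.78 − 1.32 = 1.46 points below the estimate and 5.09 − 2.78 = 2.31 points above it.

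**4. Effect on detection.** With 350 live births, the lower exact limit first exceeds 2.78% at 17 cases (16 cases give 2.64%, 17 give 2.85%). If the true rate were doubled to 5.56%, the probability of 17 or more cases is:
- 0.75 with full ascertainment
- 0.69 at L = 20%, U = 20%
- 0.54 at L = 50%, U = 25%

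**5. The age window, separately.** Let b be the share of defects first recognised between 12 months and 6 years. The reported rate becomes p × (1 − b − L × U). The protocol gives no value for b. For illustration, b = 10% with complete follow-up gives 2.78% × 0.90 = 2.50%. Better infant follow-up does not remove this term.

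**6. A tempting repair that fails.** Suppose the 12-month denominator is infants with a 12-month form plus any infant with a recorded defect. This keeps lost infants whose defect was seen at birth and drops the other lost infants:

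rate = p × (1 − L × U) / [(1 − U) + U × p × (1 − L)]

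- L = 50%, U = 20%: 0.02502 / 0.80278 = 3.12%
- L = 20%, U = 25%: 0.02641 / 0.75556 = 3.50%

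Against a true 2.78% these are 12% and 26% too high, a larger error than the one being repaired.

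**The case against.** **Infants lost after birth are not unassessed.** This is correct. Table 1 collects defects at pregnancy outcome from both the obstetric and the pediatric HCP, and unknown defect status makes the pregnancy lost to follow-up. A reader might infer that the protocol declares unfollowed infants free of defects. It has no such rule. The only cases missed are defects first recognised later in infants with no later form.

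**The rule on length of follow-up already covers this.** Section 4.6.8.3 is worded generally, and further detail is left to the RAP, which is not at hand. This stands in part. But the protocol itself carries the rule into the infection analysis and not into section 4.8.4.2, where the primary estimate is fixed.

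**The live-birth denominator matches MACDP.** This is true, and it is the reason to keep that figure as the headline.

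**The comparison with MACDP is not clearly biased downward.** This stands. Under section 4.3.2 the registry counts two or more conditional defects as a case, whereas MACDP counts conditional defects only alongside a major one. That pushes the registry rate up. A reader might infer that the registry will look safer than MACDP, but the documents do not settle the net direction. Nor do they tie the age-6 limit to EUROCAT.

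**Differences from external data are already disclosed.** Sections 4.8.3.2 and 6 warn of this in general terms, and the final report will describe defects found after year one. The unequal age windows are not named beside the planned difference.

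**The effect is small.** It lies well inside the stated interval. It is nevertheless systematic, and it reduces the chance of detecting a true increase.

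**Conclusion.** The point holds in a limited form. Defects recognised through 12 months are divided by all live births, infants without pediatric follow-up remain in that denominator, and the birth-defect section makes no provision for length of follow-up. Taken alone, this lowers the estimate.

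The documents do not fix the size. Under the assumed ranges, 2.78% becomes about 2.67% to 2.43%, or 0.4 to 1.2 of 9.7 cases. This also assumes that loss is unrelated to defect status.

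The one-year limit against MACDP's age 6 is a separate downward influence of unknown size, and the broader case definition is an upward one. No claim about the net direction against MACDP is supported. This is an inexpensive improvement to the primary analysis and does not invalidate it.

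**What to change.** In section 4.8.4.2:

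1. Keep defects over live births as the headline figure.
2. Add the prevalence of defects recognised by the pregnancy-outcome report, over all live births. Its numerator and denominator then share one observation window.
3. Add a cumulative 12-month estimate that accounts for length of infant follow-up. A simpler alternative is the prevalence only among infants with a 12-month HCP form. Lost infants must not be added back because they have a recorded defect. State the assumption that loss is unrelated to defect status.
4. Beside the MACDP difference, state the one-year versus age-6 window and the broader registry case definition, with their opposite directions.

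The cost is one extra table from data already collected, and a wider interval for the 12-month figure. For example, with 25% of 350 infants lacking the form, about 263 remain (350 × 0.75 = 262.5). At 2.78% that is about 7 cases, and the exact 95% interval for 7/263 is about 1.1% to 5.4%. Neither the headline nor the data collection changes.
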